Subjects who discontinue from the study due to disease progression should have a CT scan (as described below) prior to initiation of new anti-cancer treatment, if deemed clinically acceptable.

Replace:

At the week 28/EOS visit or at the time of early discontinuation, the following assessments will be performed:

- bone marrow biopsy (only required if bone marrow involvement is identified at baseline or disease progression is identified during the treatment phase)

With:

At the EOS visit (**week 28 or 8 weeks after the last dose of IP**), the following assessments will be performed:

- bone marrow biopsy (only required if bone marrow involvement is identified at baseline **for CR confirmation; if a confirmatory bone marrow assessment is not obtained, these subjects should be considered as only having a PR**). **The bone marrow biopsy can be performed at \pm 14 days in relation to the study visit date.**

Section 10.1 Response Assessments

Replace:

Clinical disease assessments will be performed by the Investigator or sub investigator and will be submitted to the central imaging vendor, if applicable.

With:

Clinical disease assessments, **which will be performed in conjunction with physical examinations**, will be performed by the investigator or sub-investigator and will be submitted to the central imaging vendor, if applicable.

Section 10.3 Physical Examination

Replace:

Body weight (kg) will be measured without shoes or jacket. Height and weight will be determined at baseline.

With:

Body weight (kg) will be measured without shoes or jacket. Height and weight will be determined **within 8 days of visit 1**.

Section 10.6 Clinical Laboratory Testing

Add:

Serology (local laboratory): **HBsAg**, hepatitis B core antibody, and HCV antibody.

Section 16 REFERENCE LIST

Remove:

**A RANDOMIZED, DOUBLE-BLIND STUDY EVALUATING THE EFFICACY,
SAFETY AND IMMUNOGENICITY OF ABP 798 COMPARED WITH
RITUXIMAB IN SUBJECTS WITH CD20 POSITIVE B-CELL NON-HODGKIN
LYMPHOMA (NHL)**

SUMMARY OF CHANGES

Test Drug: ABP 798

Protocol Number: 20130109

EudraCT number: 2013-005542-11

Study Phase: 3

Date and Version: 4.0, 24 June 2016

Key Contact:

Amgen Inc.:

██████████
Clinical Research Study Manager
Amgen Inc.
[name]
[name]
[name]

Phone: ██████████
Email: ██████████

Clinical Research Organization (CRO):

██████████ PhD
Senior Project Director
PRA Health Sciences
[name]
[name]

Phone: ██████████
Mobile: ██████████
Email: ██████████

Safety Contact:

PRA Drug Safety Center

North America
[contact]
[contact]
E-mail: [contact]

Europe, Asia, and Pacific Region
[contact]
[contact]
[contact]

This study will be conducted in compliance with the protocol, Good Clinical Practice (GCP) as set forth in the International Conference on Harmonisation (ICH) guidelines on GCP (ICH E6), and applicable local regulatory requirements.

This document is a confidential communication of Amgen, Inc. Acceptance of this document constitutes agreement by the recipient that no unpublished information contained herein shall be published or disclosed without prior written approval, except that this document may be disclosed to the appropriate Institutional Review Board(s)/Independent Ethics Committee(s) under the condition that they keep it confidential.

CONFIDENTIAL

Rationale:

This amendment is issued to make the following changes:

- To make minor, non-substantive grammatical and typographic corrections (changes not detailed in this summary)
- To update Amgen key contact information
- To update International Council for Harmonisation (ICH) terminology
- To add a citation in support of rituximab monotherapy
- To modify the Inclusion Criteria:
 1. To specify the biopsy sites for histologic confirmation
 2. To extend the window for histologic confirmation to 12 months to conform to standard of care for non-Hodgkin lymphoma (NHL)
 3. To extend the window for bone marrow biopsy to 12 months to conform to standard of care
 4. To eliminate the need for subjects to undergo a bone marrow biopsy within 12 months if they previously had a bone marrow biopsy with a positive result
 5. To correct the nodal or extranodal mass size according to Groupe d'Etudes des Lymphomes Folliculaires (GELF) criteria
 6. To specify splenic enlargement according to GELF criteria should be assessed by computed tomography (CT)
 7. To specify the site of serous effusions according to GELF criteria
 8. To elaborate on the specific nature of GELF B symptoms
- To specify the dose of ABP 798/rituximab will be calculated based on height and weight obtained at baseline, and that the dose will remain the same throughout the study
- To add stopping criteria for infusion-related reactions
- To add additional monitoring requirements for infusion-related hypersensitivity reactions
- To specify investigational product dispensation delegation to maintain treatment blinding
- To detail the conditions for use of a non-contrast CT for disease burden assessment
- To allow for a 3 day window for collection of baseline hematology and serum chemistry parameters

- To specify the timeframe for randomization (within 8 days before the baseline visit)
- To specify that clinical disease assessments should be performed by the investigator or sub-investigator

1. INTRODUCTION

This statistical analysis plan (SAP) describes the statistical methods to be used during the reporting and analyses of data collected under Amgen Inc. Protocol 20130109, titled “A Randomized, Double-Blind Study Evaluating the Efficacy, Safety, and Immunogenicity of ABP 798 Compared with Rituximab in Subjects with CD20 Positive B-cell Non-Hodgkin Lymphoma (NHL).”

This SAP should be read in conjunction with the study protocol and electronic Case Report Forms (eCRFs). This version of the plan has been developed using the protocol dated 07 January 2016 version 3.0 and eCRFs dated 17 SEP 2014. Any further changes to the protocol or eCRFs may necessitate updates to the SAP.

The SAP is to be developed in two stages. The purpose is to “finalize” a SAP so that programming can start earlier in the process. Versions of the SAP up to initial sponsor approval will be known as SAP1. SAP1.1 is issued to reflect protocol version 3.0. Changes following approval of SAP1.1 will be tracked in the SAP Change Log and a final version of the SAP, known as SAP2, will be issued for Amgen’s approval prior to database lock.

2. STUDY OBJECTIVES

2.1 PRIMARY OBJECTIVE

The primary objective for this study is to evaluate the efficacy of ABP 798 compared with rituximab.

2.2 SECONDARY OBJECTIVES

The secondary objective is to assess the pharmacokinetics (PK), pharmacodynamics, safety, tolerability, and immunogenicity of ABP 798 compared with rituximab.

3. STUDY DESIGN

This is a randomized, double-blind study in adult subjects with Grade 1 or 2 follicular B-cell non-Hodgkin lymphoma (NHL) and low tumor burden. Approximately 250 subjects (125 per treatment group) will be randomized (1:1) to receive investigational product (IP) (ABP 798 or rituximab) at a dose of 375 mg/m² administered as an intravenous (IV) infusion once weekly for 4 weeks followed by dosing at weeks 12 and 20. Tumor assessment will be performed at baseline and weeks 12 and 28. Subjects will be stratified by geographic region and age (> 60 vs. ≤ 60 years).

The primary efficacy endpoint is the risk difference of the overall response rate by week 28. Response to treatment will be assessed according to 1999 IWG-NHL criteria (Cheson et al,

1999). Investigators will assess the status of each subject's follicular B-cell NHL at baseline and weeks 12 and 28. Assessment will include physical examination and radiographic examination. Copies of all scheduled and unscheduled screening and on-study computed tomography (CT) scans performed to monitor or diagnose NHL must be submitted to the central imaging vendor, Perceptive Informatics, Inc. See the Independent Review Charter for details on the independent review of the imaging and clinical data.

A subject will remain on study until week 28. Subjects who discontinue IP before week 20 will be followed for 8 weeks after the last dose of IP and then complete the end of study visit.

An independent data monitoring committee (DMC) will evaluate the safety data throughout the study, including an initial safety review after the first 12 subjects have received at least 2 doses of IP. No formal interim analysis is planned.

3.1 SAMPLE SIZE CONSIDERATIONS

Approximately 250 subjects will be randomized in a 1:1 ratio to receive ABP 798 or rituximab.

3.2 RANDOMIZATION

Approximately 250 subjects will be randomized in a 1:1 ratio via Interactive Voice or Web Response System (IXRS) to receive IP (either ABP 798 or rituximab).

Randomization will be stratified by geographic region (Eastern Europe, Western Europe/Other, North America, Japan) and age (> 60 vs. ≤ 60 years).

Assignment to the treatment arms will be based on a computer-generated randomization schedule created before the start of the study. The randomization schedule will be generated using a permuted block design within each stratum. IXRS data is integrated into the electronic data capture (EDC) system for subject enrollment. IXRS data is then imported for external data reconciliation.

A third party vendor, ALMAC Clinical Technologies, will be responsible for generating the randomization scheme and managing the randomization activities of this study.

4. STUDY VARIABLES AND COVARIATES

4.1 PRIMARY VARIABLE

The primary endpoint of the study is the RD of ORR by week 28.

4.2 SECONDARY VARIABLES

4.2.1 Efficacy

The secondary efficacy endpoint is RD of ORR at week 12.

4.2.2 Pharmacokinetics

The PK endpoints are serum concentrations at predose and immediately after the end of infusion at week 12.

4.2.3 Pharmacodynamics

The pharmacodynamics endpoints include:

- Percent of subjects with complete depletion of CD19+ cell count from baseline to study day 8
- Total immunoglobulin G (IgG) and immunoglobulin M (IgM) levels.

4.2.4 Safety

The safety endpoints include the following:

- Treatment-emergent adverse events (AEs)
- Treatment-emergent serious adverse events (SAEs)
- Clinically significant changes in laboratory values and vital signs
- Incidence of anti-drug antibodies (ADA)
- On-study progression-free survival (PFS)
- On-study overall survival (OS)

4.3 TERTIARY VARIABLES

Other variables that will be summarized are:

- Exposure to IP
- Concomitant medications.

4.4 PREDETERMINED COVARIATES AND PROGNOSTIC FACTORS

Unless stated otherwise, the following stratification factors will be adjusted as covariates in the model, be used as stratification variables in stratified analysis, or be used to examine efficacy in subgroups:

- Geographic region (Eastern Europe vs. Western Europe/Other vs. North America vs. Japan),
- Age (> 60 vs. ≤ 60 years)

Primary analyses that are intended to evaluate the treatment effect will be based on the IXRS stratification values, regardless of the subject's eCRF stratification values. For subgroup analyses where the subgroup factor is a stratification variable, an analysis similar to the primary analysis (except the inclusion of the subgroup factor) should be done for each subgroup defined by the eCRF values of the subgroup factor.

In addition, the following baseline covariates may be used for further exploration in subgroups or in multivariate analyses:

- Follicular lymphoma international prognostic index (FLIPI) (low, intermediate, high)
- Presence of B symptoms (yes vs. no)

5. DEFINITIONS

5.1 GENERAL

Actual Treatment Received

Defined according to the majority of doses received.

Change From Baseline

Change from baseline is defined as (value at post-baseline visit – value at baseline).

Disease Duration

The disease duration is the number of months from the date of original diagnosis of NHL to the date of randomization, which will be derived based on the table below. No imputation will be done for disease diagnosis date, but to avoid a disease duration of zero, 1 month may be added.

Table 1. Calculation for Disease Duration

Observed Portion	Missing Portion	Formula to Calculate Duration
Year, Month, Day		(Date of Randomization – Date of Diagnosis + 1)*12/365.25
Year, Month	Day	[Year (Date of Randomization) – Year (Date of Diagnosis)]*12 + [Month (Date of Randomization) – Month (Date of Diagnosis)]*
Year	Month, Day	[Year (Date of Randomization) – Year (Date of Diagnosis)]*12*

*If the duration equals 0, add 1 month.

Dose Delay

A dose will be considered delayed when the IP administration eCRF indicates that a dose was given but a reason for dose delay is present.

Dose Withheld

A dose will be considered withheld when the IP administration eCRF indicates that no dose is given and a reason for dose delay is present.

Duration of IP exposure

Duration of IP exposure in weeks will be defined as (end of study date – date of first dose of IP + 1) / 7.

Follicular Lymphoma International Prognostic Index and Risk Categories

The follicular lymphoma international prognostic index (FLIPI) is based on the following 5 prognostic factors:

- Age (≥ 60 years)
- Ann Arbor Disease Stage (Stage III-IV, Stage III includes IIIE, IIIES, and IIIS)
- Hemoglobin level (<120 g/L)
- Serum lactate dehydrogenase level ($>$ upper limit of normal)
- Number of nodal sites (> 4)

Subjects with 0-1 risk factors are defined as low risk, subjects with 2 risk factors are defined as intermediate risk, and subjects with 3 or more risk factors are defined as high risk.

Study Baseline

For safety endpoints, the study baseline is defined as the last non-missing assessment taken prior to the first dose of IP. In cases where baseline assessments are taken on the same day as IP and

no times are reported, it will be assumed that these assessments are taken prior to IP being administered. For subjects who are randomized but not dosed after the randomization, the baseline is defined as the last non-missing assessment prior to or on the date of randomization.

For efficacy endpoints, baseline is defined as the last non-missing assessment prior to or on the date of randomization.

Study Day

Study day 1 is defined as the first day that IP is administered to the subject. The day before study day 1 is referenced as study day -1. The study day of a given assessment is calculated as (date of assessment – first dose date of IP + 1).

Study Investigational Product

Study IP is referred to as ABP 798 or rituximab.

Study Randomization

Study randomization is defined as when the subject receives a random treatment allocation via the IXRS system.

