12.6.5 Pharmacokinetics

The 90% CI for the geometric mean ratio (GMR) of test (ABP 798)-to-reference (rituximab) for serum concentrations at predose (trough) and immediately after the end of infusion at week 12 will be calculated. Point estimates and CIs for the GMR will be estimated from an analysis of covariance model. The analysis will be conducted on the safety analysis set according to actual treatment received. Additional details on the PK analysis will be provided in the SAP.

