5.4 SAFETY

Event of Interest (EOI)

An EOI is defined as a noteworthy event for a particular product or class of products that a sponsor may wish to monitor carefully. It could be serious or non-serious, and could include events that might be potential precursors or prodromes for more serious medical conditions in susceptible individuals (Council for International Organizations of Medical Sciences (CIOMS) VI, 2005). The EOIs that will be monitored in this study are:

- infusion reactions
- tumor lysis syndrome
- cardiac disorders
- serious infections
- severe mucocutaneous reactions
- hematological toxicity
- progressive multifocal leukoencephalopathy
- GI perforation

AE preferred terms that are potentially representative of the EOI will be retrieved for review and analysis using the latest version of pre-specified Standardized MedDRA Queries (SMQs) if available.

Infusion reaction and tumor lysis syndrome EOIs will be summarized separately for:

- all events and
- events with onset day coincident with first IP infusion or the day after the first IP infusion.

If no SMQ is available for use as a search tool for a given EOI (e.g, infusion reactions) a customized search strategy will be developed and the preferred terms used in that search will be provided in an appendix to the SAP prior to the database lock.

Exposure-adjusted Incidence Rates of Adverse Events

Exposure-adjusted incidence rate is calculated as the number of subjects in a treatment group that experienced the event at least once divided by the total subject exposure times in the group. For subjects who experience the event, the exposure time is calculated as the time from the first dose date of IP to the onset of the first event. For subjects who do not experience the event, the exposure time is calculated as the time from the first dose of IP to the minimum of the end of study (EOS) visit date and death date.

Last Known Date Alive

The last known date alive will be the maximum of: end of study date, non-fatal AE start and stop dates, IP administration dates, serum chemistry and hematology sample collection dates, ADA sample collection dates, concomitant medication dates, vital sign dates, PK sample collection dates, and NHL lesion assessment dates.

Overall Survival (OS)

On-study OS is defined as the time from randomization to the date of death. Subjects who have not died before the week 28/EOS visit will be censored for OS at the last known date alive on or prior to EOS.

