6.2 PER PROTOCOL SET

The per protocol (PP) analysis set is a subset of the FAS which includes subjects who have completed all 4 weekly IP doses or who permanently ended IP prior to completing 4 weekly IP doses due to reasons allowed per protocol (ie, disease progression, adverse events and death), had at least one post-baseline tumor assessment, and did not experience a protocol deviation that would affect their evaluation for the primary objective of the study. The protocol deviations that affect evaluation for the primary objective will be determined based on a blinded data review prior to database lock.

Analyses for the PP analysis set will be based on actual treatment received.

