6.3 SAFETY ANALYSIS SET

The safety analysis set includes all randomized subjects who received at least 1 dose of IP.

All safety analyses will be conducted on this analysis set according to actual treatment received.

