9.8 SAFETY ANALYSES

All safety analyses will be performed on the safety analysis set based on a subject's actual treatment received.

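### The first-infusion event tables and the day-8 CD19+ endpoint are assigned by the product given over the whole course, although only dose 1 can have produced the result

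*SAP*

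**What the plan says.** The whole definition of actual treatment in SAP 5.1 is: "Defined according to the majority of doses received". Neither document adds a rule for an even split, for the product in use when an event starts, or for tabulating subjects who received both products.

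The definition reaches widely. SAP 6.3 states: "All safety analyses will be conducted on this analysis set according to actual treatment received". SAP 9.8 repeats this. SAP 6.2 extends it to the per-protocol set: "Analyses for the PP analysis set will be based on actual treatment received". Protocol 12.6.5 applies actual treatment to PK, and Protocol 12.6.6 applies it to the pharmacodynamic endpoints.

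Entry to the safety set is broad: "The safety analysis set includes all randomized subjects who received at least 1 dose of IP". The course is "once weekly for 4 weeks followed by dosing at weeks 12 and 20", which is six doses at most, so a subject in the safety set may have had anything from one to six.

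SAP 5.4 asks for a separate summary of infusion reactions and tumor lysis syndrome limited to "events with onset day coincident with first IP infusion or the day after the first IP infusion". SAP Appendix 3 lists these as Tables 14-6.1.23, .25, .27 and .29.

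Complete CD19+ depletion from baseline to day 8 is a named pharmacodynamic endpoint (SAP 4.2.3). Protocol 9.3 places the week-2 sample before that visit's infusion.

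**The concern.** The rule and the time window of these analyses do not match. The majority rule looks at the whole course. The first-infusion tables and the day-8 CD19+ result look at a period in which only dose 1 has been given. For a subject who received one product throughout, the two agree. For a subject whose dose 1 differed from the rest, the rule can place an event under a product that the subject had not yet received.

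The plan itself allows for mismatches: it defines actual treatment and lists actual against randomized group (SAP 9.1). Protocol 8.5.4 says that the containers differ and that an unblinded pharmacist or designee prepares each infusion, so an error at a single dose is possible. At stake is the attribution of early reactions, which the SAP singles out for separate tables in a comparison of two products.

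**Working it through.** The documents give no figure for this point, so there is nothing to reproduce. The check applies the rule to each possible case and then sizes one misattributed subject.

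**Step 1. Dose 1 alone is the wrong product.** Inputs: 1 to 6 doses (SAP 3 and 6.3) and the majority rule (SAP 5.1).

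| Doses received | Dose-1 product : other product | Arm under the rule | First-infusion event |
|---|---|---|---|
| 1 | 1:0 | dose-1 product | correctly attributed |
| 2 | 1:1 | none | no arm defined |
| 3 | 1:2 | other product | counted under a product not yet received |
| 4 | 1:3 | other product | same |
| 5 | 1:4 | other product | same |
| 6 | 1:5 | other product | same |

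The day-8 CD19+ sample follows dose 1 and precedes dose 2, so the same table applies to it.

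**Step 2. Even splits in general.** With at most six doses, the splits without a majority are 1:1, 2:2 and 3:3. A single error can produce only 1:1. A 2:2 split needs two wrong infusions in one subject, and 3:3 needs three.

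**Step 3. Size.** Assumptions: 125 subjects randomized per arm (SAP 3). Of those randomized to rituximab, *k* were given ABP 798 at dose 1, had a first-infusion reaction, and went on to a majority of rituximab. All others have event rate *p* on either product. The documents give neither *p* nor *k*.

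- By dose-1 product: difference = (125p + k)/(125 + k) − p
- By majority rule: difference = 125p/125 − [(125 − k)p + k]/125

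For k = 1 and p = 5%:

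- Dose-1 product: 7.25/126 − 6.2/124 = 5.75% − 5.00% = +0.75 points
- Majority rule: 6.25/125 − 7.2/125 = 5.00% − 5.76% = −0.76 points
- Shift: 0.75 + 0.76 = 1.51 points

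| Assumed event rate p | Shift, k = 1 | Shift, k = 3 |
|---|---|---|
| 5% | 1.51 points | 4.51 points |
| 30% | 1.12 points | 3.32 points |
| 70% | 0.48 points | 1.42 points |

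Within one arm, the k = 1 shift is about 0.75 points at 5%, 0.56 at 30% and 0.24 at 70%. The simple figure 1/125 = 0.8 points is therefore an upper value, approached only when events are rare.

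**The case against.** The strongest reply is that this is a narrow drafting gap with controls around it. It needs a dispensing error, and the documents report none and give no error rate. Protocol 8.5.4 and 8.5.5.2 provide for unblinded preparation, accountability checks and a record for each subject. The SAP plans an actual-versus-randomized list (9.1), lot numbers by subject (9.3.1) and an administration listing (16-2.4). One arm assignment for all safety tables also keeps the denominators constant. The table shells and the protocol deviation guidance are separate documents that are not available here, so a footnote rule in either cannot be excluded.

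Much of this stands, and it keeps the point small. It does not remove it, because the listings reveal a mismatch without changing the arm in any table.

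The case against also rules out several stronger readings that a reader might infer:

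- *Every reaction to a wrong first infusion is charged to the other product.* It is not. A subject who receives no further dose, for example after the Grade 4 reaction described in Protocol 8.5.6.2, is assigned to the product infused.
- *Ties are a broad problem.* Beyond 1:1 they need repeated errors in the same subject.
- *A tie would have to be settled with the events in view.* SAP 1 describes the present text as SAP1.1 and provides for a final SAP2 before database lock, so a rule can still be set under blind.
- *Product per infusion is already in the lot listing.* SAP 9.3.1 promises lot numbers for each subject and does not say that they are tied to each dose.

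**Conclusion.** The point holds for the first-infusion event tables and for day-8 CD19+ depletion. In both, a stated rule gives a wrong attribution when dose 1 alone was the wrong product and 3 to 6 doses were received. The missing tie rule is a lesser matter of detail.

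The size is zero if no dispensing error occurs. Otherwise, one affected subject with a reaction moves the between-arm difference by about 1.5 points at an assumed 5% event rate and about 0.5 points at 70%. No separate figure is offered for CD19+ depletion, because the documents give no expected depletion rate.

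A reader might infer that the equivalence conclusion is exposed. It is not: the primary analysis uses the full analysis set by randomized treatment (SAP 9.5.1.1), inference is confined to the primary endpoint (SAP 9.5.3), and safety is summarized descriptively. The per-protocol ORR sensitivity analysis does use actual treatment, so it would be affected by whatever tie rule is chosen.

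**What to change.** In SAP 5.1, keep the majority rule for the general safety tables and add:

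1. Tables 14-6.1.23, .25, .27 and .29, and the day-8 CD19+ depletion summary, are assigned by the product actually given at dose 1.
2. Every subject who received both products is listed with the product at each dose.

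As a minor clarification, set a rule for even splits in SAP2 before unblinding, and state what it does to the per-protocol ORR analysis. The rule should not default to ABP 798 without a reason. In a 1:1 subject whose first infusion was rituximab, that default would charge a rituximab reaction to ABP 798 in the general tables.

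The cost is SAP wording and a small change to table programming. Denominators may differ by one or two subjects between the first-infusion tables and the rest, which a footnote can explain. The sponsor must also confirm that the product is traceable for each infusion. The change concerns attribution in the analysis only and touches no dose, schedule or stopping rule.
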